2.3.3.4 Cross-over and Final Assessment

At the end of the first participation period of 6 weeks, each participant will be treated using Hedrin Once Liquid gel on two occasions a week apart to ensure they enter the second half of the study louse free. This treatment period will also constitute a “wash-out” period for whichever preparation was used during the first half of the study. Immediately after washing off the second application of treatment product participants will be crossed-over to the other arm of the study and the investigator will supply the parent/care giver with the alternative anonymized study preparation (i.e. if the person initially received Octanediol 1% Solution they will be allocated placebo, or vice versa). Participants will then continue in the study for a further 6 weeks.

At the end of the 12 weeks study plus one week for cross-over (approximately one school term), i.e. they have participated in both treatment arms of the study the

investigator will conduct the final assessment, unless the participant is withdrawn sooner, i.e. they choose to withdraw or are withdrawn on safety grounds. At the final assessment, the participant's hair will be combed with a head louse detection comb and any lice found will be taped (with clear tape) into the participant's CRF. If any participants, or non-participating household members, have live lice at the end of the study they will be offered a standard of care treatment (Hedrin Once liquid gel).

All adverse events and changes in concomitant medication will be recorded in the CRF.

The Completion/Withdrawal Form will then be completed.

2.3.3.6 Assessment Analysis

Definition of "infested"

It is anticipated that during the course of the study a high proportion of participants will have encounters with head lice. It is also anticipated that the Octanediol 1% solution will have a sufficient inhibitory effect on the viability of the lice that they will not be able to establish an ongoing infestation. However, this effect is not immediate and may take effect over the course of several days. Therefore, it is quite conceivable that at some point a participant may be examined and one or more apparently viable lice may be discovered. Such an event should not be considered to be a failure of the treatment and at that stage no additional intervention should be undertaken. Instead the participant should continue with the routine and at the next examination if apparently viable lice are discovered again, especially if the numbers have increased, a therapeutic intervention using the standard of care treatment should be given.

At this point, or at any other stage of the study, if ≥ 5 adult lice are found or if any stage 1 or stage 2 nymphal lice are found, it will be considered that an infestation has established and the standard of care treatment (Hedrin Once liquid gel) will be given.

Evaluation of lice recovered

Any lice fixed into the CRF during the course of the study will be examined under the microscope to establish the sex and/or stage of development of the insects. It is expected that if lice are found during the monitoring period they will be adult or third stage nymphs that have newly migrated to the head. The presence of small lice (nymphs) will be evidence that lice had established before being found and had not been sufficiently affected by the treatment regimen that they were not inhibited from laying eggs, which in turn were not prevented from developing. All CRF pages bearing lice will be archived along with the other CRF documents, the lice fixed with tape constituting a permanent record, in much the same manner as a microscope slide.

2.3.4 Concomitant Medication

The participant should not use any other form of pediculicide treatment while taking part in the study. If the use of such treatment occurs, the participant will be withdrawn from the study.

Other medication can be prescribed in the normal way although participants requiring Co-Trimoxazole or Trimethoprim should also be withdrawn from the study.

All concomitant medicines should be listed in the CRF and any changes to such medicines, during the course of the study, recorded.

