After the treatment has been washed out on Day 7 the investigator will demonstrate application of the blinded test preparation (either Octanediol 1% Solution or placebo) to the parent/care giver. After this demonstration the investigator will provide a sufficient quantity of test preparation for the parent/care giver to use over the following period.

Participants will be assessed weekly by a member of the MEC study team who is unaware of the treatment that was applied. One day before each visit is due; the parent/care giver will be sent an SMS (text) message to remind them of the appointment. If the parent/care giver does not have a mobile telephone, a landline telephone call will be made as an alternative.

If no lice are found at the regular weekly assessments, the investigator will replenish the supply of investigative product, and collect the used bottle(s) of investigative product during the routine visit.

It is possible that lice may be found at an assessment visit. However, due to the nature of the product and its mode of action this discovery does not necessarily confirm that an infestation has been established. Consequently, on the first discovery of a louse a note will be made in the CRF but no further action will be taken that day. At the next assessment visit if any lice are found, or if at any single visit ≥ 5 adult lice or any stage 1 or stage 2 nymphal lice are found, a sample will be collected and taped into the participant's CRF. The participant will then be treated using Hedrin Once liquid gel in a similar manner to the treatment on Days 0 and 7. After the second treatment the participant will continue in the same treatment arm until completion of the six week participation period for that treatment.

At the end of six weeks each participant will be treated again using Hedrin Once liquid gel to eliminate any lice present, or that have been missed by investigators during the combing assessments. Two applications of product will be made 7 days apart, with combing during the second application to ensure no lice are present. This will constitute a "wash-out" to ensure all participants start the second arm of the study louse free as at the beginning. Each Participant will then be crossed-over to the other treatment arm of the study, i.e. anyone who received Octanediol 1% Solution initially would receive placebo or anyone on placebo would receive Octanediol 1% Solution.

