2.3.7 Withdrawals

Participants may be withdrawn from the study at any time for the following reasons:

Adverse Event:

The participant is withdrawn from the study by the Investigator because of an adverse event, whether or not the Investigator believes it to be serious or caused by the study medication, and provided that the Investigator considers it is in the participant's best interest to be withdrawn. There must be a corresponding entry on the Adverse Events and/or the Serious Adverse Events Form in this instance.

Non-compliance:

The participant is withdrawn because of failure to comply with the treatment regimen, or comply with the investigations as required, but is still accessible to the Investigator.

Drop Out:

The participant withdraws consent to continue in the study, but the Investigator would otherwise consider it appropriate for him/her to continue. The participant remains accessible to the Investigator.

Lost to Follow-up:

The participant, without explanation, fails to keep appointments as scheduled for study assessments and is not seen again despite the Investigator's effort (letter, telephone, home visit etc.) to re-establish contact.

Death:

All deaths will be treated as Serious Adverse Events and Thornton & Ross Ltd must be informed within 24 hours. All associated documentation must be completed within 3 working days. Full details will be required including a post-mortem examination if possible.

Lack of Efficacy:

The participant elects to withdraw, because the medication is not adequately effective.

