3.1.2 Efficacy

The primary endpoint is the frequency of not contracting an infestation by head lice during the course of the study, indicated by no evidence of active head louse infestation.

The main secondary endpoint will be comparison of the frequency (number) of instances of reinfestation.

The other secondary endpoints are the safety and acceptability of the Octanediol 1% Solution preparation in regular use.

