3.2 Definition of Populations to be analysed

The Per-protocol Population:

Includes all randomised participants who are treated according to the study protocol.

"Intention-to-treat" Population:

Includes all participants who consented and were treated at least once. Premature terminations, due to treatment failure, adverse events etc., are included.

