This estimate of the likely numbers in relation to application of the Octanediol 1% Solution active material for 6 weeks followed by placebo for 6 weeks assumes that the potential rate of contact and reinfestation is more or less linear so that, where it was estimated from past data that a likely reinfestation rate would be approximately 4 per week for the whole population, the possible number of new cases would be 24 over the 6 weeks of one half term, or 12 cases per treatment if neither had any effect. However, if the test preparation is effective this number of cases could be reduced by approximately 60% resulting in 5 cases. This difference offers essentially similar powering to that of a parallel group calculation, although the statistical significance would be reduced overall if the reinfestation rate were to be no greater than 4 per week.

Analytical Methods:

The primary endpoint analysis is the comparison between the Octanediol 1% Solution and placebo in the frequency of not developing an infestation, with the difference between the two study treatment arms tested using the "intention-to-treat" population. Secondary endpoint analyses will be the frequency (number) of instances of reinfestation and safety of the product and participant acceptance.

Analyses will be conducted based on both the "intention-to-treat" and the "per-protocol" populations.

As this is a cross-over study with equal numbers in each treatment arm it is appropriate to analyse efficacy using a Kaplan-Meier survival analysis. This analysis will compare the time to first infestation for each individual in each arm of the crossover, in which the time to first infestation is taken as the "survival" endpoint. This will essentially address the three first analytical tasks set out in section 3.3, although point 1. will also be addressed in other analyses.

It is not considered that censoring will present as a major issue during the first half term period and, if it does occur at all, right censoring from the second half term is the likely outcome. For these data it would be appropriate to use the log-rank test to analyse in relation to time to first infestation. Comparison of the "survival" curves would probably be more appropriate in this case using the Brand and Altman approach and hazard ratio curves rather than conventional Kaplan-Meier curves (Bland and Altman, *BMJ*, 2004, 328, 1073).

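### Withdrawal for using another louse treatment, or for lack of efficacy, is related to the primary outcome but has no stated outcome value, so infestations not yet confirmed can be lost from the comparison

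*Protocol*

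**What the plan says.** **Exits.** Section 2.3.4 forbids any other pediculicide during the study and then states: "If the use of such treatment occurs, the participant will be withdrawn from the study". Section 2.3.7 lists lack of efficacy as a reason for leaving: "The participant elects to withdraw, because the medication is not adequately effective". It also lists non-compliance: "The participant is withdrawn because of failure to comply with the treatment regimen, or comply with the investigations as required". Section 2.3.3.4, on the final assessment, describes early withdrawal more narrowly: "i.e. they choose to withdraw or are withdrawn on safety grounds".

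**Event.** Section 3.1.2 states: "The primary endpoint is the frequency of not contracting an infestation by head lice during the course of the study". Sections 1.4 and 2.3.3.6 base infestation on investigator findings: lice at two successive visits, or at any one visit five or more adults or any stage 1 or 2 nymph. For a smaller finding, section 1.4 says that "on the first discovery of a louse a note will be made in the CRF but no further action will be taken that day". Under 2.3.3.3, a confirmed infestation is treated by the study team and the participant stays in the arm.

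**Analysis.** The primary comparison uses the intention-to-treat population, for which section 3.2 says: "Premature terminations, due to treatment failure, adverse events etc., are included". Section 3.4 plans Kaplan-Meier and log-rank for time to first infestation. It does not expect censoring to be a major issue in the first half term, and adds that "if it does occur at all, right censoring from the second half term is the likely outcome". McNemar's test may be added if there is no censoring. A Wilcoxon signed rank test compares infestation counts within participants.

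**The concern.** The usual reason for a carer to buy a louse treatment is that lice were seen, and in a prevention trial a participant who finds the product ineffective has most plausibly had lice. Both exits therefore depend on the primary outcome. Kaplan-Meier and log-rank need censoring to be unrelated to the event, which would not hold here. The binary endpoint is no safer: a participant who leaves with no investigator finding could be scored as having no evidence of infestation. An exit in the first period also leaves no second-period observation for a paired test.

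At stake are the number of events, the power, and, if loss differs between products, the estimate itself. A statistical analysis plan could assign outcomes to these exits, but it could not recover weekly combing visits that were never made.

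**Working it through.** **1. The same lice under two carers.** A participant has one or two adult lice at a weekly visit.

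- The carer waits. The next visit finds lice again. The infestation is confirmed, treated by the study team and counted, and the participant continues (1.4, 2.3.3.3, 2.3.3.6).
- The carer uses a shop product within the week. The participant is withdrawn (2.3.4) before the confirming visit. Section 3.2 keeps the participant in the intention-to-treat population, but no section assigns an outcome.

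**2. The plan's own figure.** Inputs from section 3.4: 65% and 30% louse free, alpha 0.05, power 80%, 34 per treatment. Sides are not stated; two-sided reproduces the figure.

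- Hazard ratio (HR) = ln(0.65)/ln(0.30) = 0.358.
- Freedman events = (1.960 + 0.842)² × [(1 + 0.358)/(1 − 0.358)]² = 35.1.
- Total N = 35.1/(1 − 0.475) = 66.8, i.e. 67, the table cell, or 34 per treatment.
- With 34 per treatment, expected events are 34 × (0.35 + 0.70) = 35.7 and power is 80.7%.

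The calculation has no dropout allowance; section 2.3.2 provides one spare block of 10 for replacements.

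**3. Effect of losing infestations.** Let fₐ and fₚ be the shares of infestations on active and placebo that end in one of these exits before confirmation. The documents give no value, so 0 to 30% is an assumption.

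If censored:

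- Observed HR = 0.358 × (1 − fₐ)/(1 − fₚ).
- Events = 34 × [0.35(1 − fₐ) + 0.70(1 − fₚ)].
- Power = Φ(√events × (1 − HR)/(1 + HR) − 1.960).

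If scored louse free, the louse-free proportions become 1 − 0.35(1 − fₐ) and 1 − 0.70(1 − fₚ), and power is that of a two-sided comparison of two proportions with 34 per arm.

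| Share lost, active / placebo | Events | HR if censored | Power if censored | Difference if scored louse free | Power if scored louse free |
|---|---|---|---|---|---|
| 0 / 0 | 35.7 | 0.358 | 80.7% | 35.0 points | 84.0% |
| 10% / 10% | 32.1 | 0.358 | 76.5% | 31.5 | 75.0% |
| 20% / 20% | 28.6 | 0.358 | 71.5% | 28.0 | 65.4% |
| 30% / 30% | 25.0 | 0.358 | 65.7% | 24.5 | 55.6% |
| 0 / 10% | 33.3 | 0.40 | 70.1% | 28.0 | 64.2% |
| 0 / 20% | 30.9 | 0.45 | 56.5% | 21.0 | 41.0% |
| 0 / 30% | 28.6 | 0.51 | 40.9% | 14.0 | 21.2% |
| 20% / 0 | 33.3 | 0.29 | 89.3% | 42.0 | 95.1% |
| 30% / 0 | 32.1 | 0.25 | 92.5% | 45.5 | 97.8% |

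The last two rows are a false gain: the product looks better only because its failures went unrecorded.

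These are parallel-group approximations. The protocol gives no within-person correlation, so the loss in a paired analysis cannot be computed from it.

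**4. Withdrawal grounds.** Section 2.3.3.4 names choice and safety. Leaving for lack of efficacy fits under choice. Mandatory withdrawal for pediculicide use (2.3.4) and withdrawal for non-compliance (2.3.7) fit under neither.

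**The case against.** A reader might infer that these participants are censored and their infestations removed from the primary count. The documents do not say so. Section 3.4 ties censoring to no withdrawal reason, section 3.2 keeps premature terminations due to treatment failure, and an infestation confirmed before withdrawal is already an event. What stands is narrower: being in the population does not give a participant an outcome.

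A reader might also infer that the effect must be diluted because more infestations occur on placebo. That does not follow. Equal proportional loss leaves the hazard ratio unchanged under censoring and costs only events and power. A biased ratio needs unequal shares, and nothing in the documents shows which arm would lose more.

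Nor do the documents show that self-treatment will be common. Section 2.3.3.2 tells carers to report any new infestation, visits are weekly, treatment is supplied, and larger or nymphal findings are treated at once. This limits the number of such exits but does not bring it to zero.

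The strongest objection is that section 2.3.3.6 says lice seen at a single visit are not in themselves a treatment failure, because the product acts over several days. Counting every self-treatment as an event would partly contradict that. This stands, and it is why an analysis restricted to confirmed infestations is needed alongside.

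Finally, outcome rules for withdrawals often sit in a statistical analysis plan, which is not at hand here. That answers the scoring question but not the end of observation, which section 2.3.4 itself fixes.

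**Conclusion.** The point holds in limited form. The protocol ends participation on an act that is usually a response to the primary outcome, allows elective exit for lack of efficacy, and does not say whether either is an infestation. Only infestations not yet confirmed by an investigator are exposed. They may be censored informatively, scored louse free, or lost from the pair.

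If an assumed 10% to 30% are lost equally and censored, power falls by about 4 to 15 percentage points from 80.7%. Scoring them louse free costs about 9 to 28 points from 84.0%. Unequal loss moves the observed hazard ratio from 0.358 to as much as 0.51, or to as little as 0.25, at 30% in one arm. These sizes rest on the protocol's 65% and 30% rates, a parallel-group approximation and an assumed share lost. They illustrate what could happen and do not forecast it.

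**What to change.** - **Sections 2.3.4 and 2.3.7:** distinguish ending study product from ending observation. The already scheduled weekly combing visits would continue, with consent, for participants who use another pediculicide or stop for lack of efficacy. The rules on product use are for the sponsor and are not at issue here.
- **Sections 2.3.3.4, 2.3.4 and 2.3.7:** reconcile the grounds for withdrawal.
- **Sections 3.1.2 and 3.4:** prespecify that, in the intention-to-treat primary analysis, use of a non-study pediculicide because lice were seen, or withdrawal for lack of efficacy before confirmation, counts as an infestation on that date. Record the reason for any such treatment so that the rule can be applied.
- **Sensitivity analyses:** one that censors these exits, and one that uses only investigator-confirmed infestations.

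Both parts are needed, since combing after a shop treatment may find nothing even where lice had been present.

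**Cost.** This is more than analysis wording: it changes withdrawal from the study in 2.3.4 and needs matching consent text. Some visits continue after product stops, though they are already scheduled. A few transient encounters, which 2.3.3.6 does not regard as failure, or precautionary treatments would count as events; the second sensitivity analysis shows how much that matters.

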2.3.5 Adverse Events

Space will be provided in the CRF specifically for recording observed and reported adverse events. All unwanted effects, whether considered to be caused by the study medication or not, will be reported to Thornton & Ross Ltd by completing the Adverse Event form.

2.3.7 Withdrawals

Participants may be withdrawn from the study at any time for the following reasons:

Adverse Event:

The participant is withdrawn from the study by the Investigator because of an adverse event, whether or not the Investigator believes it to be serious or caused by the study medication, and provided that the Investigator considers it is in the participant's best interest to be withdrawn. There must be a corresponding entry on the Adverse Events and/or the Serious Adverse Events Form in this instance.

Non-compliance:

The participant is withdrawn because of failure to comply with the treatment regimen, or comply with the investigations as required, but is still accessible to the Investigator.

Drop Out:

The participant withdraws consent to continue in the study, but the Investigator would otherwise consider it appropriate for him/her to continue. The participant remains accessible to the Investigator.

Lost to Follow-up:

The participant, without explanation, fails to keep appointments as scheduled for study assessments and is not seen again despite the Investigator's effort (letter, telephone, home visit etc.) to re-establish contact.

Death:

All deaths will be treated as Serious Adverse Events and Thornton & Ross Ltd must be informed within 24 hours. All associated documentation must be completed within 3 working days. Full details will be required including a post-mortem examination if possible.

Lack of Efficacy:

The participant elects to withdraw, because the medication is not adequately effective.

3. ANALYSIS AND REPORTS

3.1 Definition of End Points

3.1.1 Safety

Participants will be observed and all untoward effects will be recorded, whether or not they are thought to be related to the study treatment.

Details of the recording of adverse events are shown in section 2.3.5 and 2.3.6.

3.1.2 Efficacy

The primary endpoint is the frequency of not contracting an infestation by head lice during the course of the study, indicated by no evidence of active head louse infestation.

The main secondary endpoint will be comparison of the frequency (number) of instances of reinfestation.

The other secondary endpoints are the safety and acceptability of the Octanediol 1% Solution preparation in regular use.

3.2 Definition of Populations to be analysed

The Per-protocol Population:

Includes all randomised participants who are treated according to the study protocol.

"Intention-to-treat" Population:

Includes all participants who consented and were treated at least once. Premature terminations, due to treatment failure, adverse events etc., are included.

3.3 Proposed Primary and Secondary Analyses

1. To confirm that Octanediol 1% Solution can prevent the development of a head louse infestation either by killing lice that climb onto the head or so limit their viability that an infestation does not develop.
2. To compare the efficacy of Octanediol 1% Solution with that of a placebo in the prevention of head louse infestation.
3. To compare Octanediol 1% solution with placebo in the time to first infestation.
4. To compare the number of times each participant is infested while treated with Octanediol 1% Solution compared with the number of times they are infested while treated with placebo

5. To evaluate Octanediol 1% Solution in terms of safety and acceptability.

